There is support among smokers for a menthol ban with rates of those favoring the ban higher in African Americans than in Caucasians. A nationally representative cross-sectional sample contacted by telephone found that 53% of whites and 68% of African Americans supported a ban on menthol cigarettes (13). Another survey found that overall 20% supported a ban on menthol cigarettes (with an additional 52% not expressing a strong opinion) with the level of support higher among Hispanics (36%) and African Americans (29%) (14). As reported previously, our preliminary study found high levels of support for banning menthol cigarettes even after finding it difficult to abstain from menthol cigarettes over a four week period. We did not determine support for a smoking ban prior to menthol smokers switching to non-menthol cigarettes and it may be that their ability to switch to non-menthol cigarettes (despite the difficulty in doing so) resulted in greater support for a menthol ban. The proposed study would determine if support for a ban does in fact increase when menthol smokers switch to non-menthol cigarettes. This is important data that needs to be collected in that it may suggest that support for a ban on menthol cigarettes would increase after its enactment.

Although surveys of menthol smokers suggest that a substantial number would attempt to quit if menthol cigarettes were unavailable (2, 14, 15), our preliminary data found that relatively few in fact made a cessation attempt (only 3 out of 31 subjects). However, our study was not recruiting smokers specifically interested in cessation. It is not known at this time if among those interested in cessation, switching to non-menthol cigarettes (as our preliminary data suggests menthol smokers would do in the event of a menthol ban) would result in greater cessation success. Clearly, if smoking cessation success rates were to increase following a menthol ban, the health effect of such a policy would be favorable. However, since it is not known if this would occur, research is needed to obtain data on the

consequences of a ban on menthol cigarettes in order to ensure that banning menthol cigarettes would not undermine smoking cessation rates.

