Innovation: Although much research has been conducted on the epidemiology and health effects of menthol cigarettes and studies have compared cessation rates among those who prefer menthol vs. non-menthol cigarettes, there is currently little information regarding how smokers of menthol cigarettes would adjust their tobacco use if their preferred cigarettes were no longer available. It seems likely that studies comparing quit rates in those who naturally prefer menthol vs. naturally prefer non-menthol cigarettes may underestimate the beneficial effect of menthol smokers first switching to non-menthol cigarettes prior to a cessation attempt since they would be switching to a non-preferred product and therefore perhaps more likely to quit tobacco use completely. Obtaining data determining if this is indeed the case is critical considering that over 25% of all smokers and over 80% of African American smokers are currently using menthol cigarettes. Our proposed study in which African American menthol cigarettes smokers will switch to non-menthol cigarettes prior to a cessation attempt is innovative in that it attempts to approximate what is likely to happen to smoking cessation success rates were the FDA to ban menthol cigarettes.

Specific Aims/Study Objectives:

In follow-up to our previous study demonstrating that when African American menthol smokers were asked to abstain from menthol cigarettes, they switched to non-menthol cigarettes, were generally supportive of a ban on menthol and experienced an increase in motivation to quit smoking, we are proposing a follow up study to determine if switching to non-menthol cigarettes is an effective first step to cessation. We propose to study the following specific aim:

Determine the impact of a ban on menthol cigarettes on smoking cessation success rates in African American menthol smokers

We hypothesize that a) switching to non-menthol cigarettes before a quit attempt will improve cessation success. We further hypothesize that switching to non-menthol cigarettes prior to cessation will b) increase motivation and self-efficacy to quit and c) enhance support for a ban on menthol cigarettes. We anticipate that no greater harm will result from the elimination of menthol cigarettes.

Research Design and Methods:

Sampling Plan

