of using any nicotine or tobacco product. If subjects ask specifically about e-cigarettes, they will be told they can be used as long as they report their use at the next visit. Since e-cigarettes would be available to smokers were menthol cigarettes to be banned, to most closely mimic naturalistic conditions we will not ask subjects to abstain from e-cigarettes. However, since the risks of e-cigarette use are unclear as are their impact on cigarette cessation, we will also not encourage their use. In order to approximate what would likely occur were a menthol ban to be enacted, no specific instructions will be given to subjects about how to effectively quit but subjects will be encouraged to call the Smoking Quitline to obtain support for their cessation attempt. At each visit, exhaled carbon monoxide concentrations will be measured and subjects will complete questionnaires assessing craving and withdrawal symptoms, smoking urges, perceived health risk, and motivation to quit smoking. Subjects will also complete a food diary to assess menthol intake from sources other than cigarettes. A questionnaire assessing level of support for a menthol ban will be assessed at baseline, the week 0 (i.e. their quit day) visit and post-quit visits. At the baseline visit subjects will set a quit date which will be the day of their week 0 visit (i.e. they are not to smoke after the visit). If subjects wish to quit smoking the next day, that will also be allowed. At each visit, subjects will return all unused study product. In order to encourage smokers to bring back all unused product, subject payment will increase by the market value of the brand of cigarettes that they received (i.e. currently about \$8 per pack for most brands) based on how much they return. Since subjects will be provided cigarettes during the first month, they will not receive additional compensation (although parking will be provided). Returned cigarettes may be provided to the same subject as part of their subsequent supply but will not be used for any other subjects.

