Time to lapse: The primary outcome, time to lapse following the week 0 visit, will be evaluated using a two-sided log-rank test. Since drop-outs could be more likely to lapse, we will perform two tests: one censoring drop-outs at the time of their last visit, and one considering drop-outs as lapsed at the time of their last visit. Randomization of 140 subjects should balance the groups with respect to potential confounding factors, and therefore no adjustment for other factors is planned. The same procedure will be used for the secondary outcome of time to relapse.

Other outcomes: Several continuous outcomes will be measured at baseline and subsequent time points, such as motivation and self-efficacy to quit, support for a menthol ban, severity of craving, perceived health risk, urinary cotinine concentrations, and exhaled CO. We will first calculate the change in each subject's outcome from baseline to the week 26 visit, and compare the study groups using two-sided, two sample t-tests. This will provide a straightforward comparison of whether cessation of menthol use affects long-term nicotine use and perceptions. Second, we will use analysis of variance (ANOVA) with repeated measurements to further analyze trends over all visits in the study period, with group, time, and interaction effects. This would identify more precisely when particular changes took place, or if any group differences emerged around the quit attempt but diminished by the end of the study. Changes in tobacco product use within groups will be summarized qualitatively and by descriptive statistics such as proportions.

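### Hypotheses (b) and (c) concern switching before the quit attempt, but their only focused between-arm test is at week 26; no week 0 contrast is named

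*Combined protocol and SAP*

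**What the plan says.** **Hypotheses.** Specific Aims/Study Objectives states: "We further hypothesize that switching to non-menthol cigarettes prior to cessation will b) increase motivation and self-efficacy to quit", and adds as (c) that switching will increase support for a ban. The Background discussion of interest in a ban says: "The proposed study would determine if support for a ban does in fact increase when menthol smokers switch to non-menthol cigarettes".

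**Exposure and visits.** Under Implementation Plan, baseline is week -4 and the quit date is week 0. Assigned cigarettes are supplied for those four weeks. Follow-up runs to week 26.

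**Measurement.** Baseline and Pre-Quit Visits says: "A questionnaire assessing level of support for a menthol ban will be assessed at baseline, the week 0 (i.e. their quit day) visit", and also at the visits after quitting. The same section opens by listing motivation and self-efficacy among the measures for baseline and pre-quit visits. Its later list of questionnaires for every visit includes motivation but not self-efficacy.

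**Analysis.** Data Analysis, Other outcomes, covers these measures together with craving, perceived health risk, cotinine and exhaled CO. The first step is: "We will first calculate the change in each subject's outcome from baseline to the week 26 visit", and then to "compare the study groups using two-sided, two sample t-tests". The stated purpose is to learn "whether cessation of menthol use affects long-term nicotine use and perceptions". The second step reads: "we will use analysis of variance (ANOVA) with repeated measurements to further analyze trends over all visits in the study period". The model's terms are arm, visit and their interaction. One stated use is to see "if any group differences emerged around the quit attempt but diminished by the end of the study".

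**The concern.** The randomised difference in assigned product exists for four weeks and ends at week 0. The hypotheses ask what that period of switching does to motivation, self-efficacy and support for a ban. The direct measure is the change across it, from week -4 to week 0, compared between arms. The plan names no such comparison.

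The one comparison with a named visit and a named test is at week 26. By then both arms have been through the same quit attempt, participants have been free to choose their own products, and some data will be missing. A score for motivation or self-efficacy to quit at that point comes from a mixture of abstainers and people who have relapsed. It therefore reflects how the quit attempt went as well as what the switch did.

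At stake is a clear answer to (b) and (c). If an effect is present at week 0 and fades, the focused test may have little power to show it. The reader would then have to find it in a group-by-time analysis, with no visit singled out in advance.

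**Working it through.** **1. Timing.** The assigned period runs from week -4 to week 0. Week 26 is 26 - 0 = 26 weeks after it ends and 26 - (-4) = 30 weeks after baseline.

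**2. Number of visits in the ANOVA.** From baseline on: weeks -4, -3, -2, 0, 1, 2, 4, 6, 8, 12 and 26, which is 11 visits. With two arms, the interaction has (2 - 1) × (11 - 1) = 10 degrees of freedom if all are used. Support for a ban is scheduled at baseline, week 0 and the seven later visits, so 9 visits and 8 degrees of freedom.

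**3. The plan's own power figure.** Power and Sample Size gives 140 randomised 1:1, about 15% dropout, 120 with time-to-lapse data, a 0.05 cutoff, and 80% power at 0.6 SD for continuous secondary outcomes. For a two-sided two-sample test with n per arm and standardised difference d:

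power ≈ Φ(d × √(n/2) - 1.96)

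With n = 60 and d = 0.6: 0.6 × √30 = 3.286; 3.286 - 1.960 = 1.326; Φ = 0.908. The noncentral t gives 90.3%. The stated 80% is thus conservative for 120 evaluable. It corresponds to n = 2 × (1.960 + 0.842)² / 0.6² ≈ 44 per arm (45 by the t distribution), or 88 to 90 in total. With 60 per arm, the effect detectable with 80% power is about 0.52 SD. A week 0 test needs no more participants.

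**4. Illustration for week 26.** Assumptions, none given by the documents:
- The true difference at week 0 is 0.6 SD. This borrows the plan's detectable effect; it is not an expected effect.
- A fraction of it persists to week 26.
- There are 60 per arm at week 0, and either 60 or 44 per arm at week 26.

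The 60 uses the plan's 120. The summary of changes also gives a goal of at least 120 completers. The 44 is purely illustrative: Follow up visits expects six-month retention to be harder but gives no figure.

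Noncentral t, two-sided 0.05:

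| Fraction persisting | d at week 26 | Power, 60 per arm | Power, 44 per arm |
|---|---|---|---|
| 100% | 0.60 | 90.3% | 79.5% |
| 75% | 0.45 | 68.6% | 55.1% |
| 50% | 0.30 | 37.1% | 28.5% |
| 25% | 0.15 | 12.9% | 10.7% |

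The normal formula agrees for 60 per arm: 0.45 × 5.477 - 1.960 = 0.505, Φ = 0.693; 0.30 × 5.477 - 1.960 = -0.317, Φ = 0.376; 0.15 × 5.477 - 1.960 = -1.138, Φ = 0.127.

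With no decay and no extra loss of participants, week 26 has the same power as week 0. The loss comes mainly from decay, and less from missing data.

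**The case against.** The strongest answer is that the plan already foresees this. It says the repeated-measures model should show when changes occurred and "if any group differences emerged around the quit attempt but diminished by the end of the study". A reader might infer that an effect at week 0 would go unexamined and be reported as absent. The documents do not support that, because the second planned analysis is aimed at this very pattern. What remains is that it is an omnibus analysis with no week 0 contrast.

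Second, the plan sets no hierarchy between the two analyses, and the hypotheses name no visit. The words about timing in (b) say when switching happens, not when the outcome is read. A reader might see a contradiction between hypotheses and analysis. There is none: the week 26 test has its own stated long-term purpose, and the Background also values support that grows after a ban.

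Third, one might call the week 26 comparison distorted by quit status. That goes too far. Among those observed it is a randomised comparison of the total effect, including any effect that runs through quitting. It answers a different, legitimate question.

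Fourth, the power figures depend on assumed persistence, and the early effect may be small. The pilot rise in motivation (5.3 to 6.3 over four weeks) was uncontrolled, in smokers not recruited for interest in quitting. This trial requires at least 7 out of 10 for motivation at entry, so if the outcome uses that scale there is limited room to rise. This stands, and is why the table is an illustration only.

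**Conclusion.** The point holds as a gap in focus. Hypotheses (b) and (c) have no prespecified focused test at the end of the period in which the arms differ by assignment. They have a week 26 test and an omnibus model over about 11 visits.

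Its size cannot be fixed from the documents. If a 0.6 SD effect at week 0 were to persist in full, nothing would be lost with 60 per arm at week 26. If half persisted, power would fall from about 90% to about 37%, and if a quarter persisted, to about 13%. These values rest on the assumed effect, persistence and numbers observed.

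The matter is confined to three secondary outcomes; time to lapse is unaffected. It is still worth correcting, because the schedule already places support for a ban and motivation at both ends of the switch.

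**What to change.** In Data Analysis, Other outcomes, prespecify the between-arm comparison of change from baseline (week -4) to week 0 as the test of hypotheses (b) and (c), for motivation, self-efficacy and support for a ban. Use either a two-sided two-sample t-test or a named contrast in the repeated-measures model, and say which.

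Keep change to week 26 as the long-term (durability) comparison for these three outcomes. Leave it as it stands for cotinine, exhaled CO, craving and perceived health risk. Keep the repeated-measures analysis.

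Confirm that self-efficacy is completed at week 0 and make the two lists in Baseline and Pre-Quit Visits agree.

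The cost is a few sentences, with no added visits or participants. If self-efficacy has not been collected at week 0, the new test cannot be done for that outcome in participants already past the visit. The small downside is that week 26 becomes secondary for these three outcomes.

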c) *Preliminary data - Switching menthol smokers to non-menthol cigarettes:* In an open-label study, 31 African American menthol cigarettes smokers (smoking ≥ 8 cigarettes per day) completed a study in which they were asked to abstain from smoking menthol cigarettes for a 4 week period. Subjects were seen at a screening visit, a baseline visit and 1 week, 2 weeks and 4 weeks after stopping smoking menthol cigarettes. Subjects were given no specific instructions regarding how to cope with the inability to smoke menthol cigarettes (as would be the case if a menthol ban were enacted). All subjects reported switching to non-menthol cigarettes with three subjects making a smoking cessation attempt during the 4 week period. At the conclusion of the study, subjects were asked to rate on a 10 point scale how difficult it was to quit menthol cigarettes (1=easy; 10=hard) and the extent to which they were supportive of banning menthol cigarettes (1=not supportive; 10= very supportive). Subjects indicated that quitting menthol cigarettes was difficult (average score = 7.2); nonetheless motivation to quit increased slightly during the period (5.3 at baseline vs. 6.3 at week 4, $p=0.03$). Based on a preliminary analysis, upon switching to non-menthol cigarettes, participants smoked slightly fewer cigarettes over the 4 week period (12.0 cigarettes per day during the week prior to baseline vs. 10.6 during week 4, $p=0.14$) and had lower exhaled carbon monoxide concentrations relative to baseline (16.0 ppm at baseline vs. 13.2 ppm at week 4, $p=0.05$). At the conclusion of the study, subjects were generally supportive of banning menthol (average score = 7.1). These data suggest that a simulated ban on menthol likely did not result in any greater harm than continued menthol cigarette smoking (i.e. smoking did not increase and motivation to quit was not reduced). Furthermore, after experiencing a simulated menthol ban, menthol smokers were supportive of banning menthol cigarettes. The pilot study did not assess if there was in fact benefit, as would be the case if switching to non-menthol cigarettes resulted in increased subsequent smoking cessation rates. Such an outcome would be consistent with research studies finding that cessation rates are generally higher for African American non-menthol smokers relative to African American menthol smokers.

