Design Overview: This study will randomize 140 African American menthol cigarette smokers to receive either menthol cigarettes (i.e. continue smoking menthol cigarettes) or non-menthol cigarettes for a four week period. At the conclusion of the four week period, participants will attempt to quit smoking all cigarettes and will return for follow-up over a 6 month period. Tobacco use, nicotine use, motivation and self-efficacy to quit, nicotine craving and withdrawal measures and support for a ban on menthol cigarettes will be assessed during the study period. Urine cotinine concentrations will be measured at each visit. The primary outcome in this study is time from cessation to the first smoking lapse.

Subjects: In order to be eligible for this study, subjects must: 1) be African American (based on self-identification); 2) smoke primarily menthol cigarettes (greater than 80% of cigarettes smoked are menthol); 3) be between the ages of 18 and 64; 4) Smoke on average, at least 8 cigarettes per day for a period longer than 1 year and 5) express an interest in quitting smoking (rate themselves ≥ 7 on a 10 point scale assessing motivation to quit smoking). Subjects will be excluded if they have: 1) A current unstable medical / psychiatric condition as determined by self-report; 2) Substance abuse within six months of beginning the study based on self-report; 3) Regularly use any form of nicotine or tobacco other than cigarettes or 4) Are pregnant or breast feeding based on self-report (subjects will

be given a urine pregnancy test at the screening visit with pregnancy later in the study and breast feeding based on self-report).

As the risks associated with the study procedures are small, all medical assessments are based on self-report (except for a urine pregnancy test at screening).

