Screening Visit: All subjects will undergo a screening visit prior to enrollment at which written informed consent will be obtained and eligibility will be verified. Medical and psychiatric history will be obtained via subject report. Baseline questionnaires assessing smoking history and nicotine dependence will be administered. Exhaled carbon monoxide (CO) will be measured to confirm that they are smokers (CO \geq 8 ppm) with a NicCheck performed (with a cut-off of ≥ 5) for those who state that they smoke \geq 8 cigarettes per day but for whom CO is less than 8 ppm (e.g. they didn't smoke that morning, they are coming from a smoke free work environment, etc.). Subjects that qualify and are interested in participating will be asked to maintain a smoking diary for the duration of the study and will be scheduled for the baseline visit.

Baseline and Pre-Quit Visits: Smoking behavior subsequent to the screening visit will be determined as will subjects' level of craving, withdrawal, perceived health risk, motivation and self-efficacy to quit smoking and support for a menthol ban. At the baseline visit subjects will be told their randomization and given appropriate product (i.e. menthol or non-menthol cigarettes, based on randomization) at no cost to them for a total of 4 weeks. Subjects will be given a quantity of cigarettes equivalent to approximately 120% of their average daily use based on smoking diaries collected at the baseline visit or at pre-quit visits up to a maximum of approximately 1.5 packs per day. Since cigarettes packs generally contain 20 cigarettes, these percentages are approximations subject to rounding. This amount is chosen in case smoking increases as a result of switching to non- menthol and to allow for flexibility in scheduling subjects for subsequent visits (i.e. if a visit is delayed by several days, subjects will still have product). Subjects will be asked to smoke only study product for the 4 week period following the baseline visit. They will be given no specific instructions regarding using medicinal nicotine (i.e. nicotine patch, gum) or the use of e-cigarettes but will be asked to record any instances

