At all visits, subjects will be asked to provide a urine sample. The urine will be used to measure cotinine concentrations and may in the future also be used to measure other markers related to smoking menthol cigarettes (such as other nicotine metabolites, menthol concentrations, tobacco toxicants, etc.). Subjects will also be asked to bring in their smoking diary in which they are to record cigarettes smoked as well as any other tobacco or nicotine products used (including e-cigarettes).

Follow up visits: Starting at Week 0 (quit date); subjects will attend follow up visits at weeks 1, 2, 4, 6, 8, 12 and 26. At each of these visits subjects will be asked if they have smoked at all since their previous visit. Exhaled carbon monoxide (CO) will be measured with an exhaled CO less than 8 ppm and a urine cotinine concentration of less than 50 ng/ml confirming abstinence (16). Smoking diaries will be used to determine time to lapse (time from their quit attempt until any smoking occurs) and time to relapse (time from their quit attempt until the first day of seven consecutive days that a cigarette is smoked).

Subjects will be paid \$20 for the screening visit, \$30 for each of the 7 visits between week 0 and week 12 with a \$100 bonus if they complete all visits up to week 12 and have complied with study related procedures. We anticipate that it will be more difficult to retain subjects through the 6 month visit; therefore subjects will receive \$60 for that visit. Since it is imperative that subjects honestly report any smoking during the study (in order to calculate time to lapse), payment during the cessation phase will not be contingent on successful abstinence. Subjects that relapse and resume smoking during the study will still be eligible to continue in the study. However, subjects that fail to follow study procedures (e.g. provide urine samples, fill out questionnaires, etc.) will be removed from the study.

Data and Safety Monitoring Plan:

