Power and Sample Size: Our primary outcome is time to lapse. Previous studies have found that during a cessation attempt most participants lapse within one week, at a median of 2-3 days after their quit attempt (35, 36). We plan on enrolling 140 subjects randomized 1:1 with an approximately 15% post-randomization visit dropout rate, leaving 120 subjects with data on time to lapse. This gives us over 80% power to detect a 1.7-fold difference using a significance cutoff of 0.05. We believe that such a difference would be a meaningful indicator of smoking success. The 1.7 fold difference in time to lapse is substantially smaller than is typically seen with medication studies. For example, an analysis by Shiffman et al (J Consult Clin Psychol 2006;74:276-85) found that the median duration of abstinence (i.e. time to lapse) was 6 days for active nicotine patch and 2 days for placebo. That would correspond to a 3 fold difference. Directly comparable data for other interventions is not available, however in a study comparing placebo to five different pharmacotherapy options (i.e. bupropion, nicotine lozenge, patch, bupropion + lozenge, patch + lozenge), the time until 50% of participants in the placebo group lapsed was approximately 6 days whereas the time for all other groups (except for nicotine lozenge) the time until 50% of participants lapsed was over 20 days (Japuntich et al. J Consult Clin Psychol 2011;79:34-42), an over 3-fold difference. Likewise, we

would have 80% power to detect an effect size of 0.6 in continuous secondary outcomes (i.e. a difference in group means of 0.6 times the outcome's standard deviation). Since it is not clear what the smallest difference is that would be important to detect, we believe that this sample size will be able to detect a meaningful difference.

Data and Record Keeping:

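### Week 26 continuous outcomes are compared as unadjusted change scores; adjusting for the baseline value already collected is usually more precise and costs at most about 1% of variance

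*Combined protocol and SAP*

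**What the plan says.** The Data Analysis section, under Other outcomes, covers motivation and self-efficacy to quit, support for a menthol ban, craving, perceived health risk, urinary cotinine and exhaled CO. Two analyses are planned:

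- First, the change in each participant's "outcome from baseline to the week 26 visit, and compare the study groups using two-sided, two sample t-tests". The stated reason is simplicity.
- "Second, we will use analysis of variance (ANOVA) with repeated measurements to further analyze trends over all visits in the study period". The terms listed are arm, visit and their interaction. Baseline is not named as a covariate.

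The sentence that no adjustment is planned stands in the Time to lapse paragraph and concerns confounding, not precision.

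Three other places bear on the point:

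- **Power and Sample Size** says the trial "would have 80% power to detect an effect size of 0.6 in continuous secondary outcomes", with 120 of 140 participants contributing data on time to lapse.
- **Follow up visits** says of week 26: "We anticipate that it will be more difficult to retain subjects through the 6 month visit". No retention figure is given.
- **Subjects** requires a score of at least 7 "on a 10 point scale assessing motivation to quit smoking".

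**The concern.** A change score uses the baseline value, but with a coefficient fixed at 1. If the true within-arm slope of the week 26 value on baseline is below 1, subtracting the whole baseline adds noise and over-corrects any chance imbalance. ANCOVA estimates the slope from the data. The planned test keeps its type I error rate and is unbiased under randomization, so what is at stake is precision.

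Hypotheses b (motivation and self-efficacy) and c (support for a ban) rest on these outcomes. The Power and Sample Size section admits that the smallest important difference is not known, so readers will depend on the confidence intervals, and these may be wider than the collected data require. The t-test also uses only participants with a week 26 value, at the visit where retention is expected to be hardest.

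**Working it through.** **The plan's own figure.** With 60 per arm, two-sided alpha 0.05 and a difference of 0.6 SD of the analysed variable, the noncentral t gives 90.3% power, not 80%. About 45 per arm would give 80%. The plan does not say whether 0.6 refers to the SD of the week 26 value or of the change. If it means the week 26 SD, with equal SDs at both visits, the change score has 80% at 60 per arm when the correlation is 0.32. On the first reading the stated figure is conservative, and the point here does not depend on it.

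**Inputs.** From the plan: 60 per arm (120/2), two-sided 0.05, difference 0.6. Assumed, because the documents give neither: *r*, the baseline to week 26 correlation, and *k* = baseline SD / week 26 SD. The week 26 SD is set to 1.

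**Formulas.**

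- Variance of change: 1 + k² − 2rk
- ANCOVA residual variance: 1 − r²
- Difference: (k − r)², never negative, and zero when r = k (slope r/k = 1)
- Cost of estimating the slope with n per arm: factor 1 + 1/(2n − 4), which is 1 + 1/116 = 1.0086 at n = 60 and 1 + 1/86 = 1.0116 at n = 45; one degree of freedom is also lost

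Example, k = 1 and r = 0.5: the change variance is 1 + 1 − 1 = 1.00. ANCOVA gives 0.75 × 1.0086 = 0.756, a net saving of 24%. The planned t-test would need 60/0.756 ≈ 79 per arm to match it.

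**Results, 60 per arm, difference 0.6 of the week 26 SD.**

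| k | r | Net variance saved | Power, change | Power, ANCOVA |
|---|---|---|---|---|
| 1 | 0.3 | 34% | 78.7% | 92.5% |
| 1 | 0.5 | 24% | 90.3% | 96.3% |
| 1 | 0.7 | 14% | 98.8% | 99.5% |
| 0.75 | 0.3 | 17.5% | 87.1% | 92.5% |
| 0.75 | 0.5 | 7% | 95.1% | 96.3% |
| 0.75 | 0.7 | −0.4% | 99.5% | 99.5% |
| 0.5 | 0.3 | 3% | 91.7% | 92.5% |
| 0.5 | 0.5 | −0.9% | 96.4% | 96.3% |
| 0.5 | 0.7 | 6.5% | 99.3% | 99.5% |

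**Interval width.** At k = 1, the 95% CI half-widths in week 26 SDs are 0.43 against 0.35 (r = 0.3), 0.36 against 0.31 (r = 0.5) and 0.28 against 0.26 (r = 0.7), change score first.

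**If 0.6 means the SD of change.** The planned test has 90.3% power. ANCOVA has 98.1%, 96.3% and 94.1% at r = 0.3, 0.5 and 0.7 (k = 1).

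**Lower retention.** 45 per arm at week 26 is an assumption, not a figure from the plan. At k = 1, power is 66.2% against 83.5%, 80.4% against 89.8% and 95.3% against 97.5% at the same three correlations.

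**Motivation.** If entry scores are uniform on 7, 8, 9 and 10, the baseline SD is √1.25 ≈ 1.1. For an assumed week 26 SD of 2 to 2.5, k is about 0.45 to 0.56, so the k = 0.5 rows apply and the gain is near zero.

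**Simulation.** In 20,000 trials with 60 per arm, k = 1 and r = 0.5, power was 0.905 (change) and 0.964 (ANCOVA). Rejection under the null was 0.050 and 0.052. With a true slope of 1, simulated variance ratios (ANCOVA/change) were 1.007 to 1.009, in line with the 0.86% worst case.

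**The case against.** The strongest reply is that nothing is broken. The planned test is valid, these are secondary outcomes, a change score is easy to read, and the primary analysis is untouched. In eight of the nine scenarios above the planned test exceeds the 80% target, and in six of them ANCOVA moves power by 1.2 points or less. The large gains need similar SDs at the two visits and a modest correlation, which the documents cannot confirm. The 45-per-arm case is assumed, and the list of approved changes keeps a goal of at least 120 completers. All of this stands. It makes the point one of efficiency, of uncertain size, felt mainly in interval width.

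The pilot does not settle the correlation. Its CO result ("16.0 ppm at baseline vs. 13.2 ppm at week 4", n = 31, p = 0.05), read as a paired t-test, implies an SE of 2.8/2.042 = 1.371 and an SD of change of 1.371 × √31 ≈ 7.6 ppm. With an assumed SD of 6 to 10 ppm at each visit, r = 1 − 7.63²/(2s²) runs from 0.19 to 0.71. That range is wide, and it describes 4 weeks in people not asked to quit.

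The plan calls its two analyses first and second without ranking them, and the ANOVA may include baseline as one of its time points. That is not the same as adjusting for it.

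Finally, Baseline and Pre-Quit Visits has assignment disclosed at the baseline visit and does not say that questionnaires come first. A baseline answered after disclosure would compromise both analyses. It needs clarifying but does not favour the change score.

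**Conclusion.** The concern holds as a modest, low-cost improvement. Baseline adjustment at week 26 cannot lose more than about 0.9% of variance with 60 per arm (1.2% with 45). It saves 14% to 34% if the SDs at the two visits are equal and r lies between 0.3 and 0.7. The saving shrinks when the baseline SD is smaller than the week 26 SD and vanishes where the slope is near 1. Motivation may gain almost nothing. Support for a ban has no entry cut-off, so that particular restriction does not apply to it. All sizes rest on assumed r and k. Neither the choice of week 26 nor the use of the ANOVA for the quit period is in dispute.

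**What to change.** Replace the week 26 change-score t-test with a linear model of the week 26 value on arm and the baseline value of the same outcome, and report the adjusted difference with its 95% CI. This uses the same two measurements as the planned test, so the cost is a change of wording and little programming.

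An alternative that also uses participants without a week 26 value is a mixed model on all post-baseline visits, with the week 26 arm contrast as the result. It should include:

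- **Terms:** baseline, arm, visit, arm-by-visit and baseline-by-visit. The last is needed: at k = 0.75 and r = 0.7, an assumed pooled slope of 0.6 gives variance 0.573, against 0.513 for the change score and 0.510 with the visit's own slope.
- **Covariance:** unstructured, with the week 26 ANCOVA as the stated fallback if the model does not converge. Ten post-baseline visits give 10 × 11/2 = 55 covariance parameters, fewer for outcomes collected less often.
- **Missing data:** a statement that the model assumes missing at random, and a sensitivity analysis such as delta-adjusted imputation for drop-outs. The Time to lapse paragraph already reasons: "Since drop-outs could be more likely to lapse, we will perform two tests". Extending that worry to attitude scales is a judgement, and the deltas would have to be chosen.

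This option takes more programming. A week 0 contrast from the same model could be named as an optional secondary result, since hypotheses b and c fix no visit.

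Two points of wording should be settled in either case. State that baseline questionnaires are completed before assignment is disclosed. Confirm the visits at which self-efficacy is collected: Baseline and Pre-Quit Visits opens by listing "motivation and self-efficacy to quit smoking and support for a menthol ban", but its later list of questionnaires for each visit omits self-efficacy.
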